7.3 Missing Data and Imputation Methods

Under the ITT principle, all patients who are randomized are included in the analysis. Therefore, missing data, especially in the outcome measures, can be problematic. Every effort is to be made to keep all missing data, particularly the Day 90 outcomes, to a minimum. Despite the clinical sites' best efforts, some missing data may be inevitable mainly due to lost-to-follow-up (LTFU). The number and proportion of subjects eligible for and compliant with each follow-up examination will be presented. Subjects who withdraw from the study will be tabulated with reasons for withdrawal. Since the primary endpoint is defined using mRS, subjects deceased during study follow-up will be scored as mRS 6. Other subjects not completing the 90-day follow-up visit will be categorized for the primary endpoint using the mRS as of the last available follow-up visit or discharge (whichever is later). As a sensitivity analysis, we will also perform analysis after excluding subjects without 90-day follow-up evaluations. Additional details will be provided in the Statistical Analysis Plan (SAP).

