4.4 Study Visits

Subjects enrolled in this study will follow the below visit schedule according to their institutional standard of care for stroke patient follow-up.

- Baseline
- Randomization
- 24 hours (+/-12 hours) Post-Randomization
- 7 Days Post-Randomization or Discharge (whichever comes first)
- 30 Days (+/- 14 days) Post-Randomization Follow-up
- 90 Days (+/- 14 days) Post-Randomization Follow-up

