4.8 Baseline Evaluation

Inclusion and exclusion criteria will be confirmed. Once the patient meets all eligibility criteria, and the patient or surrogate has provided written informed consent, he/she will undergo standard non-study surgical preoperative workup including but not limited to: demographic confirmation, medical history, and focused physical examination (see Table 1 for complete assessment schedule). Baseline imaging may either be CT/CTA/CTP or MRI/MRA/MRP prior to the pre-procedure DSA. The baseline neurologic examination will be performed by a health care provider or study team member, certified to administer the exam and able to give an unbiased neurological and functional assessment (pre-stroke mRS and presentation NIHSS). A pregnancy test will be conducted for applicable subjects (females <50 years old and of child bearing potential). Concomitant medications will be collected at baseline, 24 hours post-randomization, at discharge, and at follow up visits (30 days and 90 days post-randomization).

Table 1: Schedule of Events

Activity	Baseline	Randomization/Procedure	24hrs Post-Randomization	7days Post-Randomization or Discharge	30d Post-Randomization	90d Post-Randomization	Neurological Deterioration	Any Add' l FU (if needed)	Study Closure
Evaluation of Criteria									
Eligibility Labs ¹	X								
Informed Consent	X								
Randomization		X							
Past Medical History	X								
Clinical Evaluation	X		X	X	X	X	X	X	
Modified Rankin Scale	X ⁴		X ⁵	X ⁵	X ⁵	X ⁵		X	
NIH Stroke Scale	X ⁴		X ⁵	X ⁵	X ⁵	X ⁵	X	X	
Glasgow Outcome Scale			X ⁵	X ⁵	X ⁵	X ⁵		X	
Stroke Impact Scale						X			
CT/CTA or MRI/MRA ²	X		X				X		
Angiogram, TIMI/TICI scores ³		X							
Mechanical Thrombectomy Procedure ³		X							
Concomitant Medications	X	X	X	X	X	X			
Adverse Event assessment	X	X	X	X	X	X	X	X	X

¹Eligibility Labs are those required to be within a certain range as part of the inclusion/exclusion criteria list, including: pregnancy test (if applicable), INR, platelets, and creatinine.

²CT/CTA or MRI/MRA are required at baseline and 24hrs post-randomization, and any time there is a neurological deterioration (a change in NIHSS of 4 points or more) or hemorrhage.

³Only applicable to those patients randomized to receive mechanical thrombectomy.

⁴Must be completed by an unbiased healthcare provider.

⁵Must be completed by a BLINDED stroke study team member.

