5.7 Recovery and Discharge

The subject will be recovered from the treatment and discharged from the hospital as per standard practices.

At 7 Days Post-Randomization or Discharge the following will be completed by a dedicated, pre-specified Blinded Study Stroke team member not involved in the patient's treatment: neurological exams (including NIHSS, mRS, and GOS), a review of any adverse events, and a review of current medications.

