5.9 Follow-Up Examination

5.9.1 Clinical

Several clinical outcome measures were selected for this study. These were chosen on the basis of their reliability, familiarity to the neurologic community, adaptability for use in

patients who have had a stroke, and comparability to end points used in other trials of thrombolytic therapy. The modified Rankin Scale (mRS) is an overall assessment of global handicap. In the original Rankin Scale, a score of zero indicates the absence of symptoms and a score of 5, severe disability. The modified Rankin Scale adds a score of 6 for fatal outcomes. The Glasgow Outcome Scale (GOS) is a global assessment of function.[42] A score of zero on the GOS indicates a good recovery; a score of 2 moderate disability; a score of 3 severe disability; a score of 4 survival but in a vegetative state; and a score of 5, death. It has been used in previous trials assessing outcome in hemorrhagic and ischemic stroke patients. [43][43] [43] [43] [43] [43] [43] [42] [42] [38] [36][36, 35] The National Institutes of Health Stroke Scale (NIHSS) is a 42 point scale that quantifies neurologic deficits in 11 categories. Normal function without neurologic deficit is given a score of zero.

Additionally a quality of life scale outcome measure will be utilized in this study. Quality of life scales are designed to be sensitive to changes in outcome from mild and moderate stroke undetected by other outcome measures. Important parameters not fully interrogated by conventional outcome scales can be assessed by quality of life scales, including emotion, communication, cognition, and social role function. Standard measures, such as the mRS, primarily evaluate physical aspects of stroke outcome, not addressing more relevant quality of life measures. The Stroke Impact Scale (SIS) is a validated assessment of quality of life specifically in patients with stroke. [44] [39] [37][37, 36]

All 24hr Post-Randomization (mRS, GOS, NIHSS), Day 7/Discharge (mRS, GOS, NIHSS), Day 30 (mRS, GOS, NIHSS), and Day 90 (mRS, GOS, NIHSS, SIS) clinical outcome measures will be assessed by a dedicated, pre-specified Blinded Study Stroke team member with NIHSS certification and expertise with a back up person named for cases in which the blinded team member was involved in the case during the acute hospitalization. Nursing staff, patients, and their family members will be instructed not to unblind the investigators performing these assessments.

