7.6 Blinding

This study is not blinded. Blinding is difficult, if not impossible, from a clinical perspective. It is not possible to blind the Investigator who treats the patient, nor is it possible to blind the internal review committee (IRC) members. Additionally, physicians treating subjects who experience an adverse event after must know how the stroke was treated in order to effectively report the adverse event and plan further treatment. Blinding the study is not required for interpretation of study outcomes. However to avoid bias in study results, the person performing the primary outcome assessment at 90 days

must be blinded to the subject's treatment assignment and have not been associated with the care of the subject during the acute treatment phase.

8. Study Withdrawal

Subjects may be terminated or withdrawn from the study for the following reasons:

- Voluntary withdrawal of consent— meaning that a subject voluntarily chooses not to participate further in the study. All data collected up to the withdrawal of consent will be maintained in the study database.
- Lost to follow-up — defined as a subject who is more than one month late to a study visit and for whom 5 documented telephone attempts to contact the subject and at least one certified letter were unsuccessful.
- Subjects may also be withdrawn at the investigator's discretion if within their best interest.

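### Section 7.3 can carry forward an mRS from an additional follow-up visit, the only post-randomization mRS in Table 1 for which no blinded rater is required

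*Combined protocol and SAP*

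**What the plan says.** **Which value is analysed.** Section 7.3 gives deaths an mRS of 6. Other patients who do not complete the 90-day visit are scored "using the mRS as of the last available follow-up visit or discharge (whichever is later"). The rule has no condition on the type of visit or on who gave the score. A sensitivity analysis leaves out patients without a 90-day evaluation, and further detail is deferred to a SAP. The supplied text has no separate SAP section.

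**Who must be blinded.** In Table 1 (section 4.8), footnote 5 requires a blinded team member. On the mRS row it marks 24 hours, 7 days/discharge, 30 days and 90 days. Section 5.9.1 lists the same four assessments ("All 24hr Post-Randomization (mRS, GOS, NIHSS), Day 7/Discharge (mRS, GOS, NIHSS), Day 30 (mRS, GOS, NIHSS"), and then Day 90) and says that these "clinical outcome measures will be assessed by a dedicated, pre-specified Blinded Study Stroke team member". Section 5.7 repeats this for day 7/discharge, which is to be "completed by a dedicated, pre-specified Blinded Study Stroke team member not involved in the patient's treatment: neurological exams (including NIHSS, mRS, and GOS").

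**The exception.** Table 1 has a further column, "Any Add' l FU (if needed"), with an mRS entry that carries no footnote 5. Section 5.9.1 does not list that visit.

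**Purpose of blinding.** Section 7.6 says that the trial is open-label and that the treating investigator cannot be blinded. It then states the safeguard: "However to avoid bias in study results, the person performing the primary outcome assessment at 90 days" must be blinded and must not have cared for the patient in the acute phase.

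**The concern.** The blinded rater is the main protection of the primary endpoint in a trial where the treating team knows the arm. Section 7.6 attaches that protection to "the person performing the primary outcome assessment at 90 days". Section 7.3 can put a different score in that place, and nothing requires the replacement to be blinded. Suppose a patient has a blinded day-30 score, then an additional visit on day 60, and no day-90 visit. Read as written, 7.3 takes the day-60 score because it is the later one. If the treating physician gave it, a score made with knowledge of the arm displaces a blinded one in the intent-to-treat primary analysis.

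What is at stake is rater bias in the primary odds ratio, in a direction set by the rater's expectation. This is separate from whether carry-forward is a good way to handle missing data at all.

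**Working it through.** **1. Post-randomization mRS assessments in Table 1, side by side.**

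| mRS assessment | Blinded rater required? | Source |
|---|---|---|
| 24 hours | yes | Table 1 footnote 5; 5.6; 5.9.1 |
| Day 7 or discharge | yes | Table 1 footnote 5; 5.7; 5.9.1 |
| Day 30 | yes | Table 1 footnote 5; 5.9.1 |
| Day 90 | yes | Table 1 footnote 5; 5.9.1; 7.6 |
| Additional follow-up | not stated | plain entry in Table 1; absent from 5.9.1 |

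One entry lacks the requirement, and 7.3 does not exclude it.

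**2. How many patients the rule can reach.** Section 7.1 needs 180 patients and allows 10% loss: 180 / (1 − 0.10) = 200, as stated. (The 180 is also plausible. The Whitehead proportional-odds formula with OR 2.1, 80% power and an assumed two-sided 5% level gives 177 to 182 for five of six assumed control distributions, and 191 for an extreme one.) Planned loss is 0.10 × 200 = 20 patients. The documents give no rate of additional visits, so the number carrying such a score lies between 0 and about 20.

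**3. What an unblinded score could do.** All inputs in this step are assumptions:
- Control mRS 0 to 6 = 5/9/11/14/21/10/30%, with 5 and 6 collapsed as in 7.2.
- 100 patients per arm, and a two-sided 5% test.
- Carried scores occur in survivors only. A shifted score moves one category, better under thrombectomy and worse under control.

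The odds ratio is the large-sample proportional-odds fit to the shifted distributions. For the rejection rate:
- V = (N/12)(1 − Σp̄³). Without shift, Σp̄³ = 0.0782, so V = (200/12)(0.9218) = 15.36.
- Rejection = Φ(δ − 1.96) + Φ(−δ − 1.96), with δ = ln(OR) × √V.

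| Share carried | Fraction shifted | True OR 1.0 reads | Null rejection | True OR 2.1 reads |
|---|---|---|---|---|
| 2% | 25% | 1.01 | 5.0% | 2.12 |
| 2% | 50% | 1.02 | 5.1% | 2.14 |
| 5% | 25% | 1.03 | 5.1% | 2.15 |
| 10% | 50% | 1.11 | 6.8% | 2.30 |

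Last row: the shifted distributions give V = 15.34, so δ = ln(1.106) × √15.34 = 0.394. Rejection is Φ(−1.566) + Φ(−2.354) = 0.059 + 0.009 = 0.068. Simulations of 40,000 trials with a tie-corrected Wilcoxon test gave 6.6% and 6.9% for this row.

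The last row is an upper bound for these shifts. It needs all 20 expected losses to be alive, to have an additional visit later than the last blinded score, and to have an mRS recorded there by someone who knows the arm. Half of those scores must then be wrong in the same favourable direction.

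**The case against.** **The protocol may mean only scheduled visits.** Section 4.4 attaches the follow-up label only to the 30- and 90-day visits, and section 4.8 describes follow-up visits for medication recording in the same way. On that reading 7.3 can carry only day 30 or day 7/discharge, both blinded. This is a fair reading but not the only one. Table 1 itself labels the extra column as follow-up, and section 8.1 adds the word scheduled when it means a scheduled visit. The text is open on this point, so a reader should not infer that two rules flatly contradict each other.

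**Silence is not unblinding.** Table 1 does not say that the additional-visit rater knows the arm, and the named blinded member or back-up could score the visit. This stands: the gap is a missing requirement, not a documented unblinded score.

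**Discharge.** A reader might infer that discharge scores are exposed too, because 7.3 takes the later of visit and discharge while section 4.4 schedules "7 Days Post-Randomization or Discharge (whichever comes first"). The documents do not support that. Table 1, 5.7 and 5.9.1 all require a blinded rater for the day 7/discharge mRS, and no separate mRS is scheduled at a discharge after day 7.

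**The effect is small and other analyses expose it.** Patients lost to follow-up are unlikely to attend extra visits, so a share near 10% is improbable. The 7.3 sensitivity analysis and the per-protocol sample both exclude patients without a 90-day outcome. Both remarks are right. But those analyses drop every carried score, blinded or not, so they cannot isolate rater bias, and they leave the primary analysis as it is.

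**Conclusion.** The point holds in a limited form. As written, 7.3 permits an additional-visit mRS, for which no blinded rater is required, to replace an earlier blinded score as the primary endpoint value. The scheduled scores, including day 7/discharge, are protected.

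The expected effect is small. Under the assumed control distribution and one-category shifts favouring thrombectomy, a null odds ratio reads between about 1.01 (rejection about 5%) and an upper bound of 1.11 (rejection about 6.6 to 6.9%). If raters lean the other way, the bias reverses. A reader might infer from the 10% loss allowance that the type I error is materially inflated. The documents do not support that, because they give no rate of additional visits and the true number may be zero. Sample size and power figures are unaffected. This is a minor, inexpensive improvement to the primary analysis rule.

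**What to change.** 1. In section 7.3, replace the carried value by: *the mRS from the last assessment after randomization made by the blinded rater (Table 1, footnote 5)*.
2. In Table 1, add footnote 5 to the mRS in the additional follow-up column. Such a visit then counts when the blinded member or back-up scores it, and not otherwise.
3. Keep the sensitivity analysis that excludes patients without a 90-day evaluation.

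Make the change before outcomes are compared by arm, since choosing among carried scores afterwards would be open to challenge.

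The cost is one sentence and one footnote mark. No new staff are needed, because sections 5.6 and 5.9.1 already call for a named blinded member and a back-up. The downside is that a few patients will carry an earlier score, for example day 7 or day 30 instead of day 60. That score is further from the 90-day endpoint and may miss later recovery or decline. Having the blinded member score additional visits where possible limits that loss.

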7.4 Secondary Statistical Analysis

7.4.1 Secondary Outcomes

- 90-day global disability in the 6-12 hr cohort assessed via the proportion of patients achieving a mRS of 0-2
- Proportion of patients with good functional recovery for the 6-12 hr cohort as defined by mRS 0-2 at 90 days

- Mortality at 30 and 90 days
- Intracranial hemorrhage with neurological deterioration (NIHSS worsening >4) within 24 hours of randomization
- Procedure related serious adverse events (SAE's)
- Arterial revascularization measured by TIC1 2b or 3 following device use

Secondary outcome endpoints will be compared between randomized groups in an ITT fashion; with overall Type I error controlled using hierarchical testing. That is, if statistical significance is observed on the primary effectiveness endpoint, the secondary clinical efficacy endpoints will then be tested in sequential fashion each at a two-sided alpha level of 0.05, with testing ceasing once a null hypothesis cannot be rejected. The statistical tests will be performed in the order specified above.

7.4.2 Subgroup Analysis

7.4.2.1 Clinical Efficacy

- Maximum documented change in NIHSS
- Percentage of patients achieving NIHSS ≥ 10 point improvement or NISS ≤ 4
- NIHSS at Discharge/Day 7 post-randomization of thromectomy versus MT arms
- Functional independence (mRS 0-2) according to MR vs CT based selection methodology
- Functional independence (mRS 0-2) according to involved hemisphere
- Functional independence (mRS 0-2) correlated with location of vascular occlusion, vascular collateral score, NIHSS, and age
- Time at which functional independence (mRS 0-2) was achieved (Discharge/7 day, 30 day, and 90 day)
- Percentage of patients receiving hemicraniectomy

7.4.2.2 Technical Efficacy:

- Volume of cerebral infarction as measured by a CT or MRI scan at 24(+/-12)hrs post randomization
- Correlation of core infarct volume predicted by initial CT Perfusion imaging with 24(+/-12)hrs post randomization stroke infarction in subjects who achieved TIC1 2b-3 reperfusion
- Correlation of at risk penumbral volume predicted by initial CT Perfusion imaging with 24(+/-12)hrs post randomization stroke infarction in subjects who were randomized to MT
- mRS (at 90 days) of patients successfully revascularized (TIC1 2b and 3 versus TIC1 1 and 2a; TIC1 1 and 2a/b versus TIC1 3)

Subgroup analysis will be compared between randomized groups in an ITT fashion, with adjustment for multiple comparisons such that each will be evaluated at a two-sided alpha level of 0.01. Subgroup analyses are prospectively defined ancillary endpoints and will be presented descriptively. Additional details for these subgroup analyses will be provided in the Statistical Analysis Plan (SAP).

This is a multi-device clinical study where various devices may be used to treat vessel occlusion. The study is conducted with standardization of subject enrollment, data entry and adverse event reporting. All investigational sites will follow the requirements of a common protocol, data collection procedures and forms, and will utilize approved mechanical thrombectomy devices in accordance with product labeling.

7.5 Safety Analysis

7.5.1 Safety Outcomes

Several specific adverse events will be monitored throughout the study. However the primary safety outcomes to be assessed at completion of the trial are:

- Symptomatic intracranial hemorrhage at 24 hours post-randomization
- Asymptomatic intracranial hemorrhage at 24 hours post-randomization
- Intracranial hemorrhage within 90 days of hospital discharge
- Clinically significant complications (pneumonia, sepsis, UTI, etc.) at time of discharge or 7 days post randomization, whichever comes first.
- Mortality rates at 30 days post-hospital discharge
- Mortality rates at 90 days post-hospital discharge
- Treatment-related SAEs up to 48 hours post-randomization

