5.6 Post-Procedure Care

Patients randomized to the medical therapy group will receive best conventional MT for acute ischemic stroke as determined by the attending stroke physician. Standardization of medical management in both arms will occur according to the following:

- General medical management according to AHA/ASA guidelines
- Admission to monitored or intensive care unit for at least 24 hours
- Aggressive hypertensive-hypervolemic therapy should be used only in the case of symptomatic blood pressure fluctuations or if blood pressure drops below the normal range for the patient
- Antithrombotics: ASA 325 mg PO qd X 7 days (clopidogrel may be used as adjunctive therapy if indicated for cardiac disease) then per discretion of treating physician
- Close monitoring of BP and glucose with treatment according to AHA/ASA guidelines
- Follow-up imaging study required in any patient with neurologic deterioration

Neurological and functional exams will be conducted (NIHSS and mRS at a minimum) within 24 (+/-12) hours of randomization by a dedicated, pre-specified Blinded Study Stroke team member with NIHSS certification and expertise with a back up person named for cases in which the blinded team member was involved. Follow-up imaging (i.e., non-contrast CT scan) will be performed at 24 (+/-12) hours after randomization, and will be reviewed to assess hemorrhagic transformation based on ECASS definitions:

HI 1:	Small petechiae along the margins of the infarcted area without space-occupying effect
HI 2:	More confluent petechiae within the infarcted area but without space-occupying effect
PH 1:	Hematoma in <30% of the infarcted area with some slight space occupying effect
PH 2:	Hematoma in >30% of infarcted area with substantial space occupying effect

Based on previous work, only PH 2 will be defined as a clinically significant hemorrhage.

In addition, any neurological deterioration should be evaluated by urgent CT scan and other evaluations as indicated according to investigator/hospital best practice. A symptomatic intracranial hemorrhage will be defined as 24 hour CT evidence of an ECASS defined intracerebral and a 4-point or more worsening of the NIHSS score.

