15.3 Security, Privacy, and Confidentiality

VUMC employs several layers of data protection to ensure data security. The first part of security is physical protection of the hardware systems, access to which is limited to authorized personnel. By limiting access, ensuring only authorized personnel have access, and tracking all entry, we can ensure this risk is minimal. Additionally, REDCap has a built-in audit trail that tracks all user activity and changes made to the data entry fields with a date-time stamp.

16. Adverse Events

Adverse events (AE’s) may occur at any time after randomization. Pre-existing conditions (existing prior to randomization) will be documented in the subject’s medical record as part of prior medical history but will not count as an AE unless it worsens during the study. Adverse events (serious and non-serious) will be documented on an Adverse Event form. Non-serious adverse events will be recorded from randomization through hospital discharge or 7 days post-randomization (whichever is earlier). Serious adverse events will be recorded from randomization through the end of study (i.e., 90 day post-randomization follow-up).

Investigators will record characteristics of each adverse event on an Adverse Event form. Each adverse event will be judged by the Investigator as to its level of relatedness to the investigational devices and investigational procedure. In addition, the Investigator will identify the date of onset, severity and duration. Severity will be judged using the scale noted in Table 10. All adverse events will be monitored until they are adequately resolved or explained or until the subject reaches the end of the study.

Table 10. Definition of event severity for judgment by Investigator.

Term	Definition
Mild	Patient is aware of a sign or symptom, but that sign or symptom does not interfere with normal activity or symptom is both transient and resolved
Moderate	Symptoms interfere with the subject’s usual activity or symptoms require treatment
Severe	Symptom(s) cause either severe discomfort or have a significant impact of the subject’s usual activity and symptoms require treatment

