16.2 Reporting and Review of Adverse Events

To provide for consistent reporting of adverse events, serious and non-serious adverse events will be recorded on the Adverse Event form in the database. Non-serious adverse events will be recorded from randomization through Day 7 or hospital discharge (whichever occurs first). Serious adverse events will be recorded from randomization through the end of study (i.e., 90 day final follow-up visit, death, or withdrawal of consent).

In order to ensure prompt reporting of adverse events, we require that all adverse events (as well as all related study data) be entered into the REDCap database within five working days of the study team becoming aware of the event for the following timepoints: Procedure and 7 Days Post-Randomization/Discharge (whichever occurs first). For all serious adverse events (SAEs), we require that they be reported in the REDCap within 24 hours of the study site staff first being made aware of the occurrence of the SAE. The 24 hour reporting requirement for SAEs applies to all study timepoints.

Reports of serious or life-threatening adverse events will be provided to appropriate members of the TOC and the Medical Safety Monitor (MSM). The MSM will conduct an independent review of each SAE. If the MSM believes the adverse event is serious, unexpected and either definitely, probably, or possibly related to the investigational

device(s) and/or study procedures, the TOC staff forward a Safety Report (pre-filled with as much data as possible) to the clinical site Investigator to be completed with any additional information that may be relevant to the SAE. The Safety Reports will be included in the reports prepared for the DSMB. The principal investigator at each clinical site will be responsible for reporting to his/her own IRB/EC according to individual IRB/EC policies. After the submission of the initial Safety Report, the principal investigator at the corresponding clinical site will be responsible for obtaining follow-up information about the event and reporting it to the TOC.

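### The complications safety outcome stops counting at discharge, so if early discharge differs between arms the comparison mixes complication risk with observation time

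*Combined protocol and SAP*

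**What the plan says.** Section 7.5.1 states that "the primary safety outcomes to be assessed at completion of the trial are" seven items, one of which is "Clinically significant complications (pneumonia, sepsis, UTI, etc.) at time of discharge or 7 days post randomization, whichever comes first". I read this as events occurring up to that date.

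Collection follows the same clock. Section 16 says: "Non-serious adverse events will be recorded from randomization through hospital discharge or 7 days post-randomization (whichever is earlier"). Section 16.2 repeats the rule. For the serious category section 16 says: "Serious adverse events will be recorded from randomization through the end of study", which is the 90-day visit.

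The closing date belongs to the patient, not the calendar. The visit in section 4.4 is set at day 7 or discharge, whichever is sooner. On discharge, section 5.7 says only: "The subject will be recovered from the treatment and discharged from the hospital as per standard practices". The one minimum stay stated, in section 5.6 and for both arms, is "Admission to monitored or intensive care unit for at least 24 hours". Length of stay is collected in section 5.8 as a cost item.

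No section gives a fixed-day version of this outcome, a rate per day at risk, or an adjustment for length of stay.

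**The concern.** Discharge happens after randomization and depends on how the patient recovers, so treatment can move it. A patient discharged on day 3 can contribute events for 3 days; one still in hospital contributes 7. If the arms differ in how many patients leave before day 7, they are compared over different lengths of observation. A lower count in the arm leaving sooner is then partly a product of the counting rule.

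Analysis cannot fully repair this later. A non-serious urinary infection on day 5, in a patient who went home on day 3, falls outside the outcome, and sections 16 and 16.2 do not ask the site to record it. A serious pneumonia on the same day is in the SAE data but still outside the outcome. At stake is one of the trial's named primary safety comparisons, in a study where treating physicians know the assignment (section 7.6).

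**Working it through.** The plan states no expected rate, length of stay or test for this outcome, so there is no figure of its own to reproduce. From the documents I take the counting rule (7.5.1), the cut-off for non-serious events (16, 16.2) and about 100 patients per arm (200 randomized 1:1, sections 7.1 and 4.9). Everything else below is assumed.

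**Flat hazard, one discharge day per arm.** Let R be the true risk by day 7, the same in both arms and unaffected by discharge. The daily hazard is h = −ln(1 − R)/7, and the proportion counted by day t is 1 − exp(−h·t), with t the smaller of length of stay and 7. For R = 20%, h = 0.2231/7 = 0.0319. Observation to day 7 counts 20.0%. Observation to day 4 counts 1 − exp(−0.1275) = 12.0%. The apparent relative risk is 12.0/20.0 = 0.60 with no true difference. Stating the rate directly gives nearly the same: at 4% per day, 1 − exp(−0.16) = 14.8% against 1 − exp(−0.28) = 24.4%, a ratio of 0.61.

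**Falling hazard.** If the hazard halves every 2 days, put k = ln(2)/2. The cumulative hazard is −ln(1 − R)·(1 − exp(−k·t))/(1 − exp(−7k)). At R = 20% and t = 4 this is 0.2231 × 0.75/0.9116 = 0.1836, so 16.8% is counted and the ratio is 0.84.

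**Spread-out stays.** Stays are taken as lognormal with standard deviation 0.6 on the log scale, flat hazard, cut at day 7.

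| Assumed observation (longer vs shorter stay) | Apparent relative risk, R = 10% to 30% |
|---|---|
| All patients 7 vs 3 days, flat hazard | 0.44 to 0.47 |
| All patients 7 vs 4 days, flat hazard | 0.58 to 0.61 |
| All patients 7 vs 5 days, flat hazard | 0.72 to 0.75 |
| All patients 7 vs 4 days, falling hazard | 0.83 to 0.85 |
| Median stay 7 vs 4 days, spread out | 0.74 to 0.75 |
| Median stay 8 vs 6 days, spread out | 0.89 to 0.90 |
| Median stay 12 vs 10 days, spread out | 0.97 |
| Both arms at least 7 days | 1.00 |

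The risk level hardly matters; the pattern of stays and the shape of the hazard do. I place no weight on the day-3 row, which needs a whole arm to leave on day 3.

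**Chance of a misleading p-value.** The plan names no test, so this uses a two-sided 0.05 comparison of proportions, 100 per arm, R = 20%. The chance of significance in favour of the arm leaving sooner (nominally 2.5% in that direction) is about 34% for all patients at 7 vs 4 days, about 13% for spread-out medians of 7 vs 4, and about 5% for medians of 8 vs 6.

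**Risk that falls on leaving hospital.** Take 4% per day in hospital and 1% per day afterwards, with one arm leaving on day 4. The true day-7 risk in that arm is 1 − exp(−0.16 − 0.03) = 17.3%, against 24.4% in the other: a true ratio of 0.71, recorded as 0.61. Of the recorded gap of 9.6 points (24.4 − 14.8), 7.1 are real (24.4 − 17.3) and 2.5 come from the window (17.3 − 14.8).

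**Fixed day-7 window.** If all events are captured, equal true risk gives equal counts, ratio 1.00, whatever the discharge dates.

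**The case against.** The other side has good points.

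- *Size.* A ratio near 0.6 needs every patient in an arm to stop being observed on the same day, and a hazard that carries on unchanged after discharge. Milder assumptions give about 0.75 to 1.00. This stands.
- *Some of the reduction may be real.* Patients who recover faster may have fewer infections, and those sent out early may be at lower risk. The last illustration shows most of a gap could then be true. This also stands, though the Introduction cites inpatient data in which half of thrombectomy patients went to long-term care facilities, so discharge need not end the risk.
- *Serious events are kept.* SAEs are recorded to day 90, and the DSMB sees all AEs and SAEs (7.5.2.1). What is lost altogether is the non-serious events between early discharge and day 7. The serious ones still do not enter this outcome.
- *Little formally depends on it.* The outcome is not in the hierarchical testing (7.4.1), is not among the named interim items (7.5.2.1), and has no threshold. That lowers the stakes, but the plan still calls it a primary safety outcome.
- *The window matches a scheduled visit.* That is convenient, but it does not equalize observation.

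A reader might infer that thrombectomy will look safer for this reason alone. The documents do not support that: they do not say which arm leaves sooner. The hypothesized benefit makes earlier discharge after thrombectomy plausible, no more. Nor do they support the reverse inference, that intensive care after the procedure lengthens the thrombectomy stay, since section 5.6 sets the same minimum for both arms.

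**Conclusion.** The concern holds as a conditional one. As written, the outcome is observed for a time that treatment can affect. If discharge before day 7 differs between arms, the arm leaving sooner will tend to show fewer complications partly for that reason. The direction follows from the rule; the size cannot be known from the documents. With equal true risk assumed, I would quote an apparent relative risk of about 0.6 to 1.0, with 0.75 to 0.9 for spread-out stays or a falling hazard. The distortion is smaller again if risk drops on leaving hospital, or if complications themselves delay discharge, and it vanishes if both arms stay at least 7 days. It should be corrected because the outcome is labelled primary for safety and the missing non-serious events cannot be recovered afterwards. It does not touch the mRS analysis or the recording of serious events.

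**What to change.** - In section 7.5.1, count these complications from randomization to a fixed day 7 in every patient, in or out of hospital, and amend sections 16 and 16.2 to match.
- Make serious complications to day 7 the anchor of the comparison. These come from SAE records already collected for all patients to day 90.
- For patients discharged before day 7, add non-serious complications up to day 7 through a question at the AE assessment Table 1 already schedules at 30 days.
- Keep the inpatient-only count as a supportive table. Beside it, report length of stay (already collected under 5.8) and deaths before day 7 by arm, since death also ends observation and a fixed window does not resolve that.

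The cost is a wording change in three sections and one added question. The downside must be stated in the plan. Mild events after discharge would be recalled at day 30 ± 14, that is between days 16 and 44, in an open-label trial, while inpatient events have records made at the time. Some under-ascertainment linked to discharge date will remain, which is why the serious-event count should carry the comparison. Even that is not wholly free of discharge date, because section 16.1 counts prolonged hospitalization as a criterion of seriousness.
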